10.3.2 Analysis of the primary efficacy variable

10.3.2.1 Hypotheses and statistical model

Subjects will be randomized 1:1:1:1:1 to five different sequences of five study treatments according to a Latin square design [see Table 1]. The five study treatments are oral fixed doses of AC-541468 (5, 10, 25, 50 mg) and placebo.

The study is using the generalized Multiple Comparison Procedure – Modeling (MCP-Mod) approach [Bretz 2005, Pinheiro 2006, Pinheiro 2014], which combines a multiple-comparison procedure to assess the efficacy of the drug versus placebo and a modeling step to further identify the dose that is most likely to provide the expected level of efficacy (based on the primary efficacy endpoint).

The generalized approach is appropriate for this study design where each patient receives different doses in a sequence. A univariate dose-response relationship is modeled based on the mean change from baseline in WASO at each dose [see Section 10.3.2.3]. This approach has been qualified by the EMA as “*an efficient statistical methodology for model-based design and analysis of phase II dose finding studies under model uncertainty*” [EMA 2013].

The maximum mean reduction in WASO from baseline to Days 1 and 2 with an ACT-541468 dose is assumed to be 25 minutes (standard deviation = 40 minutes) larger than placebo.

The null hypothesis of an absence of a dose-response relationship for change from baseline in WASO will be tested at a two-sided significance level of 5% against the alternative hypothesis of existence of a dose response.

Dose selection to be used in future clinical trials will be done in consideration of the statistical results and clinically meaningful criteria.

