10.5 Sample size

The following sample-size calculations are based on MCP-Mod methodology [Pinheiro 2006]. Computations were performed in R version 3.1.2 using the *DoseFinding* package.

Assuming the maximum mean reduction in WASO from baseline to Days 1 and 2 with an ACT-541468 dose is 25 minutes (standard deviation = 40 minutes) larger than with placebo, and values from 8% of subjects are not available for analysis, a total sample size of approximately 50 (i.e., 10 subjects per sequence allocated in a 1:1:1:1:1 ratio) provides between 89–92% power (power is 90% when averaged over all candidate models [Figure 2]) to reject the null hypothesis of no dose response at a 5% two-sided significance level, while the alternative hypothesis is that a dose-response relationship exists.

The between-subject standard deviation in WASO across all arms is expected to be no more than 40 minutes. The sample size is conservative, since a correlation of zero (and non-negative) is assumed between assessments across dose within the same subject.

Assuming the maximum mean reduction in WASO is considered to be 20 minutes larger than with placebo, a sample size of 71 subjects (with no dropout) are required. This number decreases to 32 subjects if we consider a maximum reduction of 30 minutes compared to placebo.

This study is powered to detect a dose-response signal given the pre-defined set of candidate dose-response curves shown in [Figure 2](#). The study is not specifically powered to show the superiority of individual doses of ACT-541468 compared to placebo nor to provide a certain precision in estimation of a given target dose.

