**Figure 2 Candidate dose response models**

The following describes how the parameters (i.e.,  $ED_{50}$ ) of these models are calculated.

For the purpose of determining optimal contrasts, only the standardized form  $f^0(d, \theta^0)$  of the dose response model  $f(d, \theta) = \theta_0 + \theta_1 f^0(d, \theta^0)$  needs to be considered [Bretz 2005], i.e., the scale parameters ( $\theta_0$  and  $\theta_1$ ) are removed from the functional form.

The functional form of the  $E_{\max}$  model is defined as  $f(d, \theta) = E_0 + E_{\max} \frac{d}{ED_{50} + d}$ , where  $d$  = dose;  $E_0$  = placebo (basal) effect;  $E_{\max}$  = maximum change in effect associated with dose;  $ED_{50}$  = dose that is expected to give half of the maximum change.

The standardized form of the  $E_{\max}$  model is therefore  $f^0(d, \theta^0) = \frac{d}{ED_{50} + d}$ , which represents the percentage ( $p$ ) of the maximum change from the basal effect associated with dose ( $d$ ) (since the standardized  $E_{\max}$  model is the same as the functional form when  $E_0 = 0$  and  $E_{\max} = 1$ ). Rearranging the formula above gives  $ED_{50} = \frac{d(1-p)}{p}$ . The specification of  $ED_{50}$  will fully parameterize the standardized form of the model.

The  $ED_{50}$  for each  $E_{\max}$  model (i.e., 1.11, 3.75, 15) was calculated assuming a  $p$  of 90%, 80%, and 40% at an ACT-541468 dose ( $d$ ) of 10 mg, 15 mg, and 10 mg, respectively.

The calculation of each optimal contrast [see Section 7.3.2.1] depends on the pre-defined estimates of  $ED_{50}$  and dose levels (including placebo as 0 mg). Since three  $E_{\max}$  models are pre-specified, three different sets of testing contrasts will be determined for the  $E_{\max}$  model (family).

The functional form of the linear model is defined as  $f(d, \theta) = E_0 + \delta d$ , where  $d = \text{dose}$ ;  $E_0 = \text{placebo (basal) effect}$ . Hence, the standardized form of the linear model is a function of dose only  $f^0(d) = d$ . Since no parameter estimates  $\theta^0$  are required, the determination of the appropriate single testing contrast is derived based on dose alone.

To ensure no inflation of type I error, the pre-specified parameter values  $\theta^0$  (i.e.,  $ED_{50}$ ) are not to be changed after the blind is broken.

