#### *Second stage*

Among the candidate dose response models with a significant contrast test (i.e., adjusted two-sided  $p$ -value < 0.05) identified in the MCP step, the dose response model parameters (e.g.,  $ED_{50}$ ) are estimated by fitting the dose response model (family) to the estimates obtained from the mixed effects model ( $\hat{\mu}_d$  and  $\hat{S}$ ) in the first stage. The best fitting dose response model ( $E_{\max}$  or linear) will be selected based on the gAIC (smaller is better). This chosen dose response model will then be used to estimate the target dose.

Based on the selected dose response model, the predicted mean (95% CI) dose response profile for the change from baseline in WASO will be graphically displayed.

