#### **7.3.2.3 Dose selection based on WASO**

Estimation of a target dose (TD) will be performed on the basis of the fitted dose response model ( $E_{\max}$  or linear) chosen in the second stage. The estimated TD will be the lowest dose strength anywhere within the studied dose range (0 mg to 50 mg) which shows a clinically meaningful effect (i.e., 15 minutes better than predicted mean value of placebo) and a statistically significant effect (i.e., lower 95% CI of the predicted mean value at TD > observed mean value of placebo). Note: the choice of 95% CI is not driven by the purpose of controlling type I error rates.

To aid understanding of the accuracy/variation associated with the selected dose response model, the following parameters of interest will be derived using a nonparametric bootstrap technique.

- The 0.025, 0.5 (median) and 0.975 bootstrap percentiles of the predicted mean (on the change in reduction in WASO of ACT-541468 relative to placebo) for the chosen dose response model,
- The 0.025, 0.5 (median) and 0.975 bootstrap percentiles of the target dose defined as 15 minutes better than predicted mean value of placebo,
- The 0.025, 0.5 (median) and 0.975 bootstrap percentiles of the target dose defined as 20 minutes better than predicted mean value of placebo,
- If the  $E_{\max}$  model is selected, the 0.025, 0.5 and 0.975 bootstrap percentiles of the  $E_0$ ,  $ED_{50}$  and  $E_{\max}$  will be presented.

The nonparametric bootstrap technique will proceed as follows:

1. Sample, with replacement, the data available at each period per subject until the resampled dataset contains the same number of subjects as in the original dataset,
2. From the resampled dataset, calculate and store the parameter estimates that define the dose response model,
3. Repeat steps 1 and 2 numerous times (say 1000) to derive the bootstrap distribution for each parameter,
4. Use the bootstrap distribution to calculate the parameters of interest described above.

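### The target-dose bootstrap lists no step that repeats model selection; if Emax ED50 = 15 is true, its limits cover the true 15-minute dose in only 52–81% of trials (within-subject correlation 0 to 0.7)

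*SAP*

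**What the plan says.** SAP 7.3.2.2 (Second stage) fits the families that have a significant contrast, chooses Emax or linear by gAIC, and continues: "This chosen dose response model will then be used to estimate the target dose".

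SAP 7.3.2.3 adds a nonparametric bootstrap. Its stated purpose is "To aid understanding of the accuracy/variation associated with the selected dose response model". Its outputs include "The 0.025, 0.5 (median) and 0.975 bootstrap percentiles of the target dose defined as 15 minutes better than predicted mean value of placebo", the same for 20 minutes, percentiles of the predicted mean for the chosen model, and percentiles of E0, ED50 and Emax if Emax was selected. Step 2 reads "From the resampled dataset, calculate and store the parameter estimates that define the dose response model". Steps 1 to 4 contain no contrast test, no gAIC comparison and no model averaging. They also do not say how to count a resample whose fitted curve fails to reach 15 or 20 minutes by 50 mg.

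The SAP attaches no coverage level to these percentiles. Protocol 10.5 says the study is not specifically powered to show superiority of individual doses, "nor to provide a certain precision in estimation of a given target dose". Protocol 10.3.2.1 adds: "Dose selection to be used in future clinical trials will be done in consideration of the statistical results and clinically meaningful criteria".

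**The concern.** The family is chosen from the same data that estimate the dose. A bootstrap that keeps the family fixed measures the scatter of the parameters within that family and leaves out the uncertainty about which family is right.

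The two families place the 15-minute dose far apart. If the truth is a moderately curved Emax and gAIC picks the straight line, the fitted line understates the effect at low doses and pushes the 15-minute dose upward. Every resample refitted with a line repeats that error. The limits then look informative while excluding the true dose and the lower studied doses. The SAP prespecifies several candidates because the shape may be misspecified, so this drops shape uncertainty at the point where the dose is estimated.

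**Working it through.** **Inputs.** From Protocol 10.5: maximum effect 25 minutes over placebo, SD 40, 8% of subjects not available (50 × 0.92 = 46), two-sided 5%. SAP 7.3.1.1 places the 25 minutes at 50 mg. Doses are 0, 5, 10, 25 and 50 mg; the candidates are Emax with ED50 1.11, 3.75 and 15, and linear. For within-subject correlation (ρ) the protocol gives only the sizing assumption: "a correlation of zero (and non-negative) is assumed between assessments across dose within the same subject". The values 0.3, 0.5 and 0.7 are my assumptions.

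**Stated power first.** With 46 subjects, ρ = 0 and a critical value of 2.24 for the four contrasts, simulated power is 89.3–91.8% across the candidates, against the protocol's 89–92%.

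**True 15-minute doses.** For Emax, the maximum is 25 × (50 + ED50)/50 and the dose giving 15 minutes is 15 × ED50/(maximum − 15). For ED50 = 15 the maximum is 25 × 65/50 = 32.5, so the dose is 225/17.5 = 12.9 mg. The same formula gives 1.58 mg (ED50 = 1.11) and 4.74 mg (ED50 = 3.75). Linear gives 15/25 × 50 = 30 mg.

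**Hand check: ED50 = 15 true, linear fitted, ρ = 0.**
- True effects at 0, 5, 10, 25 and 50 mg are 0, 8.1, 13.0, 20.3 and 25.0 minutes. The mean dose is 18 mg and the sum of squares about it is 1,630.
- The least-squares slope is 732.6/1,630 = 0.449 minutes per mg, or 22.5 minutes at 50 mg.
- Its SE at 50 mg is 50 × (40/√46)/√1,630 = 7.3 minutes.
- The upper 95% limit is about 22.5 + 1.96 × 7.3 = 36.8 minutes, so the lower limit of the 15-minute dose is about 15 × 50/36.8 = 20 mg.
- To include 12.9 mg, the upper limit would have to reach 15 × 50/12.9 = 58 minutes. That needs an estimate of about 58 − 14.3 = 44 minutes, roughly 3 SE above expectation, with probability below 0.2%.

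**Simulation.** 2,500 trials × 1,000 whole-subject resamples per scenario. The 46 subjects were spread 10/9/9/9/9 over the Latin-square sequences, with complete data. The first stage had dose, period and subject effects. ED50 was searched over 0.05–75. gAIC was GLS deviance + 2p among families significant in the trial data. Results are for trials passing the MCP step; the Monte Carlo SE of coverage is at most 1.1 points.

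| Truth ED50 = 15 | ρ = 0 | 0.3 | 0.5 | 0.7 |
|---|---|---|---|---|
| gAIC picks linear | 45% | 40% | 31% | 16% |
| Coverage, 15-minute dose, family fixed | 52% | 58% | 67% | 81% |
| Coverage, 15-minute dose, re-selected | 96% | 94% | 95% | 95% |
| Coverage, 20-minute dose (24 mg), family fixed | 66% | 63% | 68% | 82% |
| Coverage, 20-minute dose, re-selected | 97% | 95% | 95% | 95% |
| Coverage, predicted effect at 10 mg, family fixed | 51% | 58% | 67% | 81% |
| Coverage, predicted effect at 10 mg, re-selected | 96% | 94% | 95% | 95% |
| Median lower limit if linear picked, family fixed | 19 mg | 22 mg | 23 mg | 25 mg |
| Median lower limit if linear picked, re-selected | 3 mg | 5 mg | 6 mg | 8 mg |
| Upper limit above 50 mg, family fixed | 62% | 57% | 47% | 27% |
| Upper limit above 50 mg, re-selected | 62% | 58% | 48% | 28% |

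Fixed-family coverage of the 15-minute dose is 95–97% when Emax was picked and at most 0.1% when linear was picked. The overall figure is therefore close to the share picking Emax: at ρ = 0, 0.55 × 0.95 ≈ 52%.

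**Other candidates.** Fixed-family coverage of the 15-minute dose at ρ = 0 / 0.3 / 0.5 / 0.7:
- ED50 = 3.75: 82 / 88 / 92 / 95%
- ED50 = 1.11: 92 / 93 / 94 / 95%
- Linear: 94 / 94 / 91 / 91%

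Re-selection gives 94–96% in all of these.

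**Robustness.** A simpler simulation without period terms gives 50 / 58 / 67 / 82% for ED50 = 15 with the family fixed. It gives 53% and 85% with 50 subjects at ρ = 0 and 0.7. Stratifying resampling by sequence gives 51, 66 and 80% fixed against 94, 94 and 93% re-selected (ρ = 0, 0.5, 0.7).

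**Resamples that miss the target.** On average 3–10% do not reach 15 minutes by 50 mg and 16–25% do not reach 20. Dropping them instead of counting them as above 50 mg moves 15-minute coverage by at most about 1.5 points.

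**The case against.** The SAP offers these percentiles as a description of the selected model and promises no coverage, and the protocol disclaims precision for the target dose. Both are true. But imprecision is a reason to show wide limits, and limits starting near 19 mg suggest the data rule out lower doses when they do not.

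Step 2 does not say in terms that selection is not repeated. If the programmer repeats it, the problem disappears. The references to a chosen and a selected model make a fixed family the natural reading, and one sentence would settle it.

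The worst figures belong to one candidate of four and to ρ = 0, which the protocol itself calls conservative. That stands: at ρ = 0.5 to 0.7 the other three candidates give 91–95%. Even at ρ = 0.7, though, coverage under ED50 = 15 is only 81%, and the sponsor prespecified that shape.

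Re-selected limits can be very wide. In a smaller run (1,000 trials × 500 resamples, ED50 = 15), 52% of them at ρ = 0 ran from 5 mg or less to above 50 mg, falling to 11% at ρ = 0.7. This is a real cost, but it reports what the data can support.

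Finally, the SAP already plans LS means and placebo-adjusted differences with 95% CIs at each dose, which do not depend on the model, and dose selection also uses clinical criteria. Both limit the consequence, but neither supplies an interval for the target dose.

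**Conclusion.** The concern holds. As written, the bootstrap omits model-selection uncertainty. If Emax ED50 = 15 is the truth, its limits miss the true 15-minute dose in 48% of significant trials at ρ = 0 (100 − 52) and in 19% at ρ = 0.7 (100 − 81). Nearly all of the shortfall comes from trials where linear was chosen and the lower limit is too high; the upper limit is essentially unaffected. Because re-selection alone restores about 95%, the missing step is the cause.

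The sizes rest on the protocol's planning values, complete data, no baseline covariate in the simulated first stage, and assumed correlations above 0. The dose-response test, its type I error, the selected model and the target-dose point estimate are not affected. The change should be made, because these percentiles are the only planned interval for the target dose; they remain one input among several to dose selection.

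**What to change.** Amend the bootstrap steps in SAP 7.3.2.3:

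- Step 1: draw whole subjects (baseline plus all periods) with replacement. Stratifying by sequence is acceptable.
- Step 2: refit the first-stage model, then repeat the gAIC choice between Emax and linear, among the families whose contrast was significant in the trial data, before computing predicted means and target doses.
- Report the share of resamples choosing each family.
- Count resamples that do not reach 15 or 20 minutes by 50 mg as above 50 mg when taking percentiles, and report their proportion.
- Keep the E0, ED50 and Emax percentiles as planned, labelled as conditional on the Emax model. Label the predicted-mean and target-dose percentiles as including model selection.

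The cost is SAP wording and a few lines of R. The downside is wider limits, mainly through a lower lower limit, which at low correlation may span most of the studied range. Upper limits above 50 mg already occur about as often with the family fixed.

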### 7.3.3 Other

The primary endpoint will also be summarized by gender and overall using descriptive statistics.

## 7.4 Supportive/sensitivity analyses

Sensitivity analyses will be conducted on the PPS if this analysis set differs from the mFAS significantly (e.g., > 10% reduction in number of subjects).

Change from baseline to Days 1 and 2 in mean WASO will also be analyzed using a linear mixed effects model with the same factors as in the main analysis with the addition of region, race, gender, and age.

If the proportion of missing WASO values is significant (e.g., > 10% of expected data points missing based on the FAS), a sensitivity analysis will be conducted using the FAS to assess the influence of missing data on the main analysis. A data point is considered missing if both WASO assessments are missing at a given visit (i.e., Baseline or Days 1 and 2 of each treatment period). After the missing data is imputed, the change from baseline to Days 1 and 2 in mean WASO will be analyzed using the same linear mixed effects model as in the main analysis. A worst case scenario for imputing missing data will be considered: If the missing post-baseline value is for a dose group other than

placebo, then the worst post-baseline value recorded for that subject on any other dose group (including placebo) will be imputed. If the missing post-baseline value is for placebo, then the best post-baseline value recorded for that subject on any other dose group will be imputed. The dose group to which the missing value is imputed is based on the assigned treatment sequence. If the baseline value is missing, then the mean of all available baseline values will be imputed. A subject missing baseline as well as all post-baseline WASO values will be excluded from this analysis.

Using the FAS, the number (%) of subjects missing both WASO assessments at Baseline (run-in period) and Visits 3, 4, 5, 6, and 7 will be presented by randomized treatment sequence and as one group (i.e., All subjects).

## **8 ANALYSIS OF THE SECONDARY EFFICACY VARIABLES**

The analysis of the secondary efficacy variable will be performed on the FAS.

### **8.1 Objective sleep onset**

The secondary efficacy endpoint relates to objective sleep onset and is assessed through the absolute change in LPS from Baseline to Days 1 and 2.

Baseline is the mean of the two PSG nights during the run-in period (V2), and Days 1 and 2 is the mean of the corresponding two PSG treatment nights for a given treatment period.

LPS is the time (min) from start of recording to the beginning of the first continuous 20 epochs (i.e., 10 min) scored as non-wake, i.e., epochs scored as either sleep stage 1 (S1), sleep stage 2 (S2), sleep stage 3 (slow wave sleep [SWS]) or rapid eye movement (REM), as determined by PSG.

The same MCP-Mod analysis as performed for the primary endpoint will be conducted to evaluate the dose response of ACT-541468 on the secondary efficacy endpoint. Three  $E_{max}$  models with an  $ED_{50}$  of 1.11, 3.75, 15, respectively, and one linear model will be considered. Summary statistics will also be provided.

## **9 ANALYSIS OF OTHER EFFICACY VARIABLES**

The analysis of other efficacy variables will be performed on the FAS.

For endpoints based on objective assessments (e.g., WASO, LPS and Total Sleep Time [TST]) as determined by PSG):

- Baseline is the mean of the two PSG nights during the run-in period (V2),
- Days 1 and 2 is the mean of the corresponding two PSG treatment nights for a given treatment period.

For endpoints based on subjective assessments (e.g., subjective WASO [sWASO], subjective Latency to Sleep Onset [sLSO], subjective TST [sTST], Sleep Quality [SQ]):

- Baseline is the mean value of the sleep diary entries during the run-in period (V2),
- Days 1 and 2 is the mean value of the corresponding sleep diary entries for a given treatment period.

### **9.1 Objective and subjective sleep maintenance**

Summary statistics will be provided for:

- Absolute values of WASO at Baseline and Days 1 and 2 by gender and overall,
- WASO over time (by hour of the night and by quarter of the night),
- Absolute values of sWASO at Baseline and Days 1 and 2 by gender and overall,
- Absolute change in sWASO from Baseline to Days 1 and 2 by gender and overall.

### **9.2 Objective and subjective sleep onset**

Summary statistics will be provided for:

- Absolute values of LPS at Baseline and Days 1 and 2 by gender and overall,
- Absolute values of sLSO at Baseline and Days 1 and 2 by gender and overall,
- Absolute change in sLSO from Baseline to Days 1 and 2 by gender and overall.

### **9.3 Objective and subjective Total Sleep Time**

TST is the amount of actual sleep time (min), i.e., time spent in epochs scored as non-wake as determined by PSG.

sTST is the self-reported time (min) spent asleep as reported in the sleep diary.

Summary statistics will be provided for:

- Absolute values of TST at Baseline and Days 1 and 2 by gender and overall,
- Absolute change in TST from Baseline to Days 1 and 2 by gender and overall,
- Absolute values of sTST at Baseline and Days 1 and 2 by gender and overall,
- Absolute change in sTST from Baseline to Days 1 and 2 by gender and overall.

### **9.4 Sleep Quality**

SQ is the sleep quality as determined by scores on the visual analog scale (VAS; mm).

Summary statistics will be provided for:

- Absolute values of SQ at Baseline and Days 1 and 2,
- Absolute change in SQ from Baseline to Days 1 and 2.

## 9.5 Sleep architecture

Absolute change from Baseline to Days 1 and 2 in the duration (min) and percentage of TST in each sleep stage (S1, S2, SWS and REM) will be summarized over the whole night, and for each quarter of the night. Absolute values will also be summarized.

Absolute change from Baseline to Days 1 and 2 in the latency (min) to each sleep stage (S1, S2, SWS, and REM) will be summarized. Absolute values will also be summarized.

